Subject Exclusion Criteria	 Advanced comorbid conditions with life expectancy <1 year Patient is <18 of years of age Patient has a CRT device Female patients who is pregnant or not on a reliable form of birth control. Women of childbearing potential are required to have negative pregnancy test within the 7 days prior to device implant Unwilling or unable to return for required follow-up visits Patient decides study participation is cost-prohibited
Duration of Exposure	At the 12-month follow-up, when each subject completes his/her cross- over 6-month therapy, the CRT (Edora HF-T QP, or Ilivia HF-T QP DF4) function will be programmed on to provide chronic benefit from CRT for a battery life of 8.6 years.
Reference therapy	Patients are self-referenced as a cross-over design.
Statistical Methodology	 The primary endpoint is the change in LVESVI. We will compare the changes in LVESVI between CRT-ON and CRT-OFF groups. We will explore 5-10 metabolomic factors as principal components to predict group differences (using a 2-sample t-test), and response to CRT therapy. In particular, we will relate these principal components to response to CRT using multiple linear regression (for the LVESVI endpoint) and Cox Regression (for the Clinical endpoint).

RESEARCH STRATEGY

A. Background and Significance

Heart failure is a progressive disease with high mortality and morbidity. Heart failure (HF) affects 5.7 million American adults and claims nearly 300,000 lives annually.¹ HF progresses along a continuum from asymptomatic (Stage A and B) to symptomatic (Stage C and D).² Nearly three times as many people with left ventricular (LV) systolic dysfunction are in Stage B as in Stages C and D combined.^{3,4} In the Framingham Heart Study, total mortality rates within four years of symptomatic HF development were 24% in women and 55% in men.⁵ In the community, the prevalence was 6% for those with a left ventricular ejection fraction (LVEF) of 50% or less and 2% for those with an LVEF of 40% or less.⁶ This translates to 4% of the population who have mild LV systolic dysfunction with LVEF between 41%-50%.⁷ Although the risk of hospitalization or death declines as LVEF increases, an LVEF in the range of 36% to 50% still confers a considerable risk of adverse outcomes. For instance, the CHARM study showed that patients with an LVEF between 33%-52% had annual cardiovascular mortality rates in the range of 4.0%-6.0% and HF hospitalization rates of 5.7%-7.2%.⁸

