We propose a single-center, randomized cross-over study design. The study will be approved by the Mayo Clinic Institutional Review Board, and a consent form will be signed by each participant. We will enroll 100 patients at Mayo Clinic, Rochester, Minnesota, who have LVEF of 35% to 50%. Of these patients, 30 will be women. Participants will undergo placement of a CRT-pacemaker (CRT-P) after the completion of the baseline assessment if all inclusion and none of the exclusion criteria are met. Participants who have an ICD in place, or who meet clinical indication for an ICD, will undergo placement of a CRT-defibrillator (CRT-D). Defibrillation will not be added for patients who do not have an existing ICD system or do not meet clinical indications for an ICD. Participants who have a successful CRT implantation will be randomly assigned 1:1 to have the CRT programmed on (CRT-ON, treatment group) or off (CRT-OFF, control group) within 7 days of completing the implant procedure. Participants will be randomly assigned using an allocation method defined by a biostatistician. Investigators managing HF in study participants will be blinded to the randomization method to minimize potential bias. A washout period after the device implantation will not be used in this study.¹⁹ At 6-month follow-up, the CRT function will be turned on in the CRT-OFF group and the CRT function will be turned off in the CRT-ON group in a cross-over design. All participants will cross-over at the 6-month follow-up visit. At 12-month follow-up, when each patient completes his/her cross-over 6-month therapy, the CRT function will be programmed on to provide chronic benefit from CRT for a battery life of 8.6 years. The subjects will be blinded from whether biventricular pacing is on or off. For participants who receive a CRT-D, the defibrillation function will be programmed on for the duration of the study.

Study device

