Peripheral venous blood samples will be collected before CRT, at 6-month and 12-month follow-up (either CRT-ON for 6-month or CRT-OFF for 6-month). At implant, blood samples from femoral artery and coronary sinus will be collected to measure transcardiac metabolomic gradient. More often, the LV lead deliver sheath for coronary sinus cannulation is able to be advanced into the beginning of lateral vein to facilitate the LV lead placement (70%-80%), where blood sample will be collected to determine the regional metabolic profile as shown in **Figure 12**. The rational for collecting the regional blood is to determine 1) whether there is a differential metabolisms between ICM (discrete scar vs no scar accessed by echocardiography) vs NICM (diffused fibrosis), and 2) metabolic feature at the most delayed conduction area at the LV lateral wall in coping with QRS-LV time.

Muscular samples collection for metabolomics measurement

When the patient is undergoing a CRT device implant, a pre-pectoral pocket is made routinely to house the generator. The skin and subcutaneous planes are dissected to expose the fascia of the pectoralis major. A small piece (0.5-1.0g) of the chest muscle (Pectoralis major) biopsy will be taken for metabolomics analysis, and mitochondrial physiology. Approximately 100mg of muscle tissue will be immediately used to evaluate mitochondrial capacity and bioenergetic efficiency using high-resolution respirometry and spectrofluorometry, as we have described previously [sup 1,2]. The remainder of the muscle tissue will be immediately blotted, frozen in liquid nitrogen, and stored at -80 C. Muscle mitochondrial content will be evaluated by laboratory-based enzymatic assays, protein expression, and mRNA abundance [sup 3]. Mass spectrometry and NMR spectroscopy will be used to detect and quantitate metabolites in muscle tissue lysates [sup 4]. Muscle biopsy may cause bleeding. We will use readily available cautery to stop the bleeding.

Device programming and follow-up

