Metabolomics data analysis. The timing of metabolomics data analysis will occur when all subjects have completed study procedures. Data sets will be mean-centered and pareto-scaled to adjust the importance of high- and low-abundance metabolites to an equal level before carrying out statistical analyses. 42,52,77-79,84-86 The SIMCA-P+ 12.0 software package (Umetrics, Umea, Sweden) will be used for pattern recognition multivariate analysis, including unsupervised principal component analysis (PCA), supervised partial least squares discriminant analysis (PLS-DA), and orthogonal partial least-squares discriminant analysis (OPLS-DA). The data will be examined with PCA scatter plot of the first two score vectors (t1-t2) in order to reveal the homogeneity of the data, any groupings, outliers, and trends. Then PLS-DA is applied to increase the class separation, simplify interpretation, and find potential biomarkers. The OPLS-DA will be used to identify the significantly different metabolites between groups. For validation, R2 (the fraction of variance explained by a component) and Q2 (the fraction of the total variation predicted by a component) values will be considered as measures of goodness of model and the model robustness, respectively. The value of Q2 ranges from 0 to 1 and typically a Q2 value of greater than 0.4 is considered a good model. Most important metabolites will be selected according to the variable importance in the projection (VIP) values and the variables with VIP>1 will be considered for significantly changed metabolites. Metabolic pathway analysis will be performed using MetaboAnalyst 3.0 software.⁸³ In addition, we will explore the new multivariate metabolomics data (80 variables on 80 subjects), and construct principal components agnostically using SAS PROC FACTOR. Preliminary data suggest that 5 to 10 factors will represent 60% or more of the joint variation among the 80 metabolites. The 5-10 factors will then be calculated on each subject, and used to predict group differences (using a two-sample t-test), and response to CRT therapy. In particular, we will then relate these principal components (PC's) to response to CRT using multiple linear regression (for the LVESVI endpoint) and Cox Regression (for the Clinical endpoint).

Safety and Adverse Events

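### The two-sample t-test for the metabolomic factors names neither the groups nor the visit, and for a CRT-ON versus CRT-OFF comparison it would give up the within-patient pairing of the crossover

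*Combined protocol and SAP*

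**What the plan says.** Two places name the test. The synopsis, under Statistical Methodology, says "We will explore 5-10 metabolomic factors as principal components to predict group differences (using a 2-sample t-test), and response to CRT therapy". The sentence just before it compares changes in LVESVI between the CRT-ON and CRT-OFF groups. The section on metabolomics data analysis describes a data set of "80 variables on 80 subjects", states that "Preliminary data suggest that 5 to 10 factors will represent 60% or more of the joint variation among the 80 metabolites", and says that the factors, once calculated for each subject, will be "used to predict group differences (using a two-sample t-test), and response to CRT therapy". Response is then related to the factors by linear and Cox regression. Neither place defines the groups, the visit, a significance level or any handling of several tests.

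The design text is explicit. The synopsis says "Patients are self-referenced as a cross-over design", and the section on study design and randomization says "All participants will cross-over at the 6-month follow-up visit". On sampling: "Peripheral venous blood samples will be collected before CRT, at 6-month and 12-month follow-up (either CRT-ON for 6-month or CRT-OFF for 6-month"). For LVESVI, the section on sample size and statistical analysis specifies a paired t-test of ON against OFF, and a secondary linear model that allows for an order effect.

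**The concern.** A patient who completes both periods has a metabolomic profile after six months ON and another after six months OFF. Two profiles from one person are normally positively correlated, and the crossover is there to exploit that. The plan does so for LVESVI. For the metabolomic factors the only group test it names is one for independent samples.

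If that test is meant for ON versus OFF, there are two ways to carry it out. All ON scores can be set against all OFF scores as if they came from different people, which uses a standard error that is too large. Or the randomized arms can be compared at 6 months only, which is valid but discards the second period. Either way, a real effect of CRT on the metabolic profile is more easily missed. The study's stated objective concerns metabolic pathways and biomarkers, so this bears on its main scientific question, although not on its primary endpoint.

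**Working it through.** **The plan's own figures first.** For the paired LVESVI test, power is P(T > t₀.₉₇₅,ₙ₋₁), where T is noncentral t with noncentrality (difference/SD)·√n. With difference 12, SD 26 and n = 100, the noncentrality is 12/26 × 10 = 4.62 and power is 99.5%, in line with the stated value of over 99%. With n = 80, the detectable difference at 80% power is 8.24 ml/m², against 8.3 stated. Both fit a two-sided 5% level, although the plan states none. It gives no power figure for the factor tests.

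**Inputs for the factor comparison.**
- n = 80 patients: from the metabolomics data analysis section.
- Each patient has one ON and one OFF sample: from the design and blood-sampling text.
- Standardized difference d = 0.35 (in between-patient SDs), two-sided 5% level, and ON/OFF correlation ρ of 0.3, 0.5 and 0.7: my assumptions; the documents give none of them.

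**(a) Paired test.** The SD of the ON-minus-OFF difference is √(2(1−ρ)), so the noncentrality is 0.35·√80/√(2(1−ρ)) = 3.130/√(2(1−ρ)), with 79 degrees of freedom.

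**(b) Two-sample test on 80 ON and 80 OFF values, pairing ignored.** The test assumes a standard error of √(2/80) = 0.158; the true one is 0.158·√(1−ρ). With critical value c = 1.975 (158 degrees of freedom), the approximations are:
- actual type I error = 2[1 − Φ(c/√(1−ρ))]
- power = 1 − Φ((c − 0.35/0.158)/√(1−ρ)) = Φ(0.239/√(1−ρ))

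| ρ | Noncentrality, paired | Power, paired | Power, pairing ignored | Actual type I error, pairing ignored |
|---|---|---|---|---|
| 0.3 | 2.65 | 74% | 61% | 1.8% |
| 0.5 | 3.13 | 87% | 63% | 0.5% |
| 0.7 | 4.04 | 98% | 67% | 0.03% |

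Simulation agrees: power of 61%, 63%-64% and 66%-67%, and type I error of about 2%, 0.6%-0.7% and 0.04%-0.06%.

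**(c) Two-sample test in period 1 only, 40 versus 40.** The noncentrality is 0.35·√(40/2) = 1.565 with 78 degrees of freedom, and power is 34%. Put as a detectable difference at 80% power, this comparison needs 0.63 SD. The paired test on 80 patients needs 0.38, 0.32 and 0.25 SD at ρ = 0.3, 0.5 and 0.7.

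**Cost of the period term.** It takes one degree of freedom (78 instead of 79). At ρ = 0.5, power stays at 87%.

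**The case against.** The strongest reply is that ON versus OFF is an inference. The metabolomics section speaks of one score per subject and uses the same scores to predict response, which fits a single baseline profile. The synopsis sentence that mentions CRT-ON and CRT-OFF is about LVESVI. The protocol also asks between-patient questions, such as women versus men and ischemic versus nonischemic cardiomyopathy, and for these a two-sample t-test is correct. Finally, a two-sample t-test of within-patient period differences between the two sequence groups is the standard period-adjusted crossover test, and the text does not exclude it.

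This stands in part. A reader might infer that the plan is wrong as written; the documents do not show that, because they never say what is compared. But a gap remains on each reading. If only between-patient groups or baseline profiles are meant, no test of the CRT effect on the factors is specified, although the objectives of metabolomic measurements invoke the crossover design for one biomarker. If the period-difference test is meant, the plan needs to say so.

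Two other inferences go too far:
- That 5-10 factors are each tested at 5%. No level is stated. If 5% is assumed and the tests are independent, the chance of at least one false positive is 1 − 0.95⁵ = 23% to 1 − 0.95¹⁰ = 40%. That applies where the two-sample test is valid, not where pairing is ignored, since there the test is conservative. The synopsis and the metabolomics section both word this analysis as exploratory, the study is labelled a pilot, and no primary or safety conclusion rests on it, so formal familywise control is optional.
- That ignoring the pairing produces false positives. With positive correlation it does the opposite.

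**Conclusion.** The point holds in a limited form. The plan leaves the groups and the visit for the factor t-test undefined, and the test it names is a poor choice for the most natural comparison in this crossover. At the assumed d = 0.35 and two-sided 5% level, ignoring the pairing costs about 13 points of power at ρ = 0.3 (74% to 61%), 24 at ρ = 0.5 (87% to 63%) and 31 at ρ = 0.7 (98% to 67%). Restricting the comparison to period 1 leaves 34%. The sizes depend on d and ρ, which the documents do not give; the direction holds for any positive ON/OFF correlation. What is affected is the exploratory metabolomic aim. The primary LVESVI analysis is already paired.

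**What to change.** In the metabolomics data analysis section, and to match in the synopsis:
- State, for each factor comparison, the groups and the visit or visits whose samples are scored.
- Test any ON/OFF comparison on the within-patient ON-minus-OFF difference in factor score with a period term, in line with the paired test and order-effect model for LVESVI. Calculate the ON and OFF scores with one common set of factor loadings so that the difference is meaningful.
- Keep the two-sample t-test for between-patient groups: sex, ischemic versus nonischemic cardiomyopathy, and responder status.
- Optionally, report p-values adjusted for the false discovery rate across the factors within each question, or label them unadjusted and exploratory.

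The cost is a few sentences and some analysis code. No new samples, visits or patients are needed. Patients without both follow-up samples add little or nothing to the paired test, so the number of complete pairs should be reported.

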glycerol/glycerol-1-phosphate ratio (mean [SD], 2.79 [1.30] than men, 1.19 [0.18]; *P*<.05) indicating lower triglyceride biosynthesis in women. The NMR data indicates that male metabolome had higher levels of N-methylhistidine and creatinine, which is associated with higher protein degradation and energetic stress.

Experimental protocol

Aim: To determine early alterations in metabolic pathways and metabolomic biomarkers in patients with mild HF and LBBB, and their role in the prediction of outcomes by early CRT.

Rationale

Reversal of myocardial dysfunction in the early stage is of great importance to prevent the progression of HF. Here we will investigate the novel use of CRT in patients who have mild HF and LBBB. This patient population is at high risk for progression from mild to severe HF. However, the metabolomics signature of mild HF with LBBB and metabolic pathways affected have not been determined.

Study Patients

Subject inclusion criteria. LVEF 35%-50%, NYHA class I-II, QRS duration of ≥120ms⁶³, LBBB⁶⁴, and on optimal and stable medical therapy (ACE inhibitor or AT1 blocker, beta blocker over the last 6-month), able and willing to sign informed consent.

Subject exclusion criteria. Advanced comorbid conditions with life expectancy <1 year, unwilling or unable to return for required follow-up visits, <18 of years of age, existing CRT device, female patients who is pregnant or not on a reliable form of birth control. Women of childbearing potential are required to have negative pregnancy test within 7days prior to device implantation.

Our preliminary studies have indicated that among 1,436 patients with LVEF of 36% to 50% and LBBB, 78 reside in Olmsted and surrounding counties, 256 reside in Minnesota, and 422 reside in nearby states and are living candidates for enrollment. In addition, as a referral center, Mayo Clinic is estimated to have approximately 80 to 100 new patients eligible for study enrollment each year.

Study design and randomization

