b. Amino acids are important substrates for energy production in the heart. Through a series of reactions, branched-chain amino acids (BCAAs) can be converted to metabolic intermediates and fed into the tricarboxylic acid (TCA) cycle as potential sources of anaplerotic input (Figure 14, red box). Due to the down regulation of gene expression related to the BCAA degradation and utilization, specifically, valine, leucine and isoleucine are accumulated in HF.^{53,81,82} Our preliminary data (shown in Figure 6 and 10), showed that the level of these BCAAs were disturbed even in mild HF and was significantly lower in CRT non-responders than in CRT responders with severe HF. Further, amino acids are not only cell building blocks, energy source and signaling molecules but are also regulators of gene expression and protein synthesis. Taken together, the BCAAs are critical metabolite markers in HF.

c. Using the new technology of whole blood ¹⁸O metabolic labeling, we will test the hypothesis that the 2,3-BPG[¹⁸O] and G-3-P[¹⁸O] turnover rates are reduced, while inorganic phosphate (Pi[¹⁸O]) and γ -ATP[¹⁸O] are elevated in mild LV dysfunction in which the impaired O2 and substrate transport and ATP synthesis may precede the HF symptoms (Figure 13).

d. We will develop strong metabolic biomarkers as proposed in above to determine the prognostication with clinical outcomes in patients with mild HF.

Primary clinical efficacy objective

The study primary endpoint is a reduction in the LV end-systolic volume index (LVESVI, reverse LV remodeling) in the CRT-ON group as compared to CRT-OFF group.

Secondary clinical efficacy objectives (composite events)

 Hospital admission for HF; 2) Increase in NT pro-BNP level by 30% and its predictive value of response to CRT; 3) Sustained ventricular tachycardia or fibrillation greater than 30 seconds; 4) Decrease in LVEF to ≤35%; and 5) death.

The analytical imprecision of natriuretic peptides depends on the assay but for NTprpoBNP it is roughly 1.6%. Inter and intradividual variation is roughly 30% (American Journal of Cardiology. 92(5):628-31, 2003). Thus values above 30% have been suggested to define significant changes in natriuretic peptides (Journal of Investigative Medicine. 61(6):950-5, 2013 Aug,). This value was shown to have prognostic significance in the VALHEFT trial (Journal of the American College of Cardiology. 52(12):997-1003, 2008 Sep 16) and thus will provide an end point in our proposed analysis.

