Primary safety objectives

Freedom from system-related complications in randomized participants will be calculated at 1, 6, and 12 months post-implant to determine the safety profile, including the device pocket hematoma, pneumothorax, myocardial perforation, lead dislodgment, lead revision, and device-related infection. This safety profile will be balanced against efficacy to quantify the risk-benefit ratio. This analysis will occur when all subjects have completed study procedures.

Sample Size Considerations and Statistical analysis

The timing of primary endpoint analysis will occur when all subjects have completed study procedures. The primary endpoint for Aim 1 is the change in LVESVI. We propose a paired t-test, which combines both

randomized groups together (n=50 + 50 = 100), and compares the CRT-ON condition to the CRT-OFF condition. The power can be estimated based on REVERSE (LVEF \leq 40%) showing a mean change of -18.4 +/- 29.5 ml/m2. Let us assume that in the current mildly impaired EF group, the reduction will be, not -18, but -12. Assuming the SD is 26, the power for the one-sample paired t-test is over 99%. If we assume an 80% attrition (n=40 + 40), the detectable difference with 80% power is 8.3 ml/m2, less than half of that observed in REVERSE. A secondary analysis will be a generalized linear model in which baseline, period 1, and period 2 values of LVESVI will be analyzed together, with the possibility of an order effect. If no order effect is detected, then the analysis will amount to the paired t-test already described. Data may be missing due to the occurrence of interim events. This would mean that the data are not missing at random. We propose to accommodate this by a rank-based procedure, in which the ON-OFF differences are ranked in both groups together. As a secondary endpoint, we will analyze the composite clinical endpoint described above. This endpoint will be analyzed as the time to the first of any of these component events. The crossover design can be accommodated by fitting the treatment variable ON-OFF as a time dependent binary variable that is 1 (ON) or 0 (OFF). Order effects can be accommodated by including interactions with time-period in the model.

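### The Cox model for metabolomic response to CRT names no component-by-ON/OFF interaction, so it measures prognosis and can mislabel a prognostic marker as a predictor of CRT response

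*Combined protocol and SAP*

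**What the plan says.** The aim of the metabolomic work covers early metabolic alterations and "their role in the prediction of outcomes by early CRT" (Experimental protocol, Aim). Under Metabolomics data analysis the metabolites are reduced to factors: "Preliminary data suggest that 5 to 10 factors will represent 60% or more of the joint variation among the 80 metabolites". The data set is described as "80 variables on 80 subjects". The factor scores are then used to "relate these principal components (PC's) to response to CRT using multiple linear regression (for the LVESVI endpoint) and Cox Regression (for the Clinical endpoint". The synopsis, under Statistical Methodology, says the same: "we will relate these principal components to response to CRT using multiple linear regression (for the LVESVI endpoint) and Cox Regression (for the Clinical endpoint". Neither place lists the other terms of the Cox model or says which blood sample supplies the scores.

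The clinical endpoint is set out under Sample Size Considerations and Statistical analysis: "This endpoint will be analyzed as the time to the first of any of these component events". That section handles the crossover by entering ON/OFF as a time-dependent 0/1 variable. The only interactions it names are with time-period, for order effects.

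Under Study design and randomization, patients are allocated 1:1 to start ON or OFF, and "All participants will cross-over at the 6-month follow-up visit". Item 3d of the Objectives of metabolomic measurements sets a second purpose for the markers: "to determine the prognostication with clinical outcomes in patients with mild HF".

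**The concern.** Predicting response to CRT and predicting outcome are different questions. The first asks whether the benefit of switching CRT on varies with the metabolic profile. The second asks whether patients with a given profile do worse, whatever the device setting.

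The analysis labelled as response to CRT regresses time to first event on the components, over follow-up of which about half is CRT-OFF. A patient who starts OFF and is admitted for heart failure in month 3 counts against the component as a failure of CRT response, although CRT was never on. As written, the response aim and objective 3d would rest on the same coefficient. A marker of sicker patients could then be presented as one that identifies who should receive early CRT.

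**Working it through.** **1. The plan's own figures.** The documents give power only for the paired LVESVI test. With n = 100, difference 12 and SD 26, the noncentrality is 12 / (26/√100) = 4.62. Power is 99.5% at two-sided 5% (the level is not stated, so it is assumed), in line with the stated figure of over 99%. With n = 80 and 80% power the detectable difference is 8.24, against the stated 8.3. Both reproduce. No event count, hazard ratio (HR) or power is given for the metabolomic Cox model.

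**2. What the coefficient measures.** Let x be a standardised component score and z = 1 when CRT is on:

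log hazard = log h0(t) + βx + γz + δxz.

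The log HR for ON versus OFF at profile x is γ + δx, so response depends on the profile only if δ ≠ 0. A model with x alone, or with x and z, estimates roughly β + wδ, where w is the share of events in ON time. If δ = 0 it estimates β, which is prognosis. Entering z as a main effect removes γ from the comparison and leaves δ untested.

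**3. Share of OFF time and OFF events.** By design the OFF share of time at risk is 6 / (6 + 6) = 50% (simulated 0.50). With an ON/OFF HR of 0.7, the OFF share of first events is about 1 / (1 + 0.7) = 59%. The documents set no explicit time horizon for this model; 12 months is assumed.

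**4. A purely prognostic marker (δ = 0), n = 80, CRT HR 0.7.** The composite's event risk is not stated. The low value of 17% is 1 − 0.83, the one-year risk of LVEF falling below 35% in the retrospective LBBB cohort (Preliminary results), which is only a partial guide. The other risks and all HRs are assumptions. Percentage of trials with p < 0.05, from 1,000 simulated trials per row:

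| Marker HR per SD | 12-month risk (events = 80 × risk) | Component only | Component + ON/OFF | Component × ON/OFF |
|---|---|---|---|---|
| 1.5 | 17% (13.6) | 30% | 29% | 4% |
| 1.5 | 30% (24) | 50% | 50% | 5% |
| 1.5 | 50% (40) | 70% | 70% | 5% |
| 2.0 | 17% (13.6) | 68% | 69% | 5% |
| 2.0 | 30% (24) | 92% | 92% | 6% |
| 2.0 | 50% (40) | 98% | 98% | 7% |

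Separate runs with other marker strengths gave, for the component main effect, 15% (HR 1.3, risk 17%), 19-21% (HR 1.3, risk 30%), 34-37% (HR 1.6, risk 17%) and 59% (HR 1.6, risk 30%). The single interaction test stayed at 4-6%.

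**5. No CRT effect at all.** With CRT HR 1.0, n = 100 and risk 30%, the component is significant in 59% (marker HR 1.5) and 96% (marker HR 2.0) of trials, although there is no response to predict.

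**6. The reverse error.** Take a marker with HR 1.5 when OFF and 1/1.5 when ON, so β = 0.405 and δ = −0.811. With CRT HR 0.7, w is about 0.7/1.7 = 0.41, and β + wδ = 0.405 − 0.334 = 0.07, close to nothing. In simulation (n = 100, risk 30%) the component-only model finds this marker in 8% of trials and the interaction in 58%.

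**7. Multiplicity of the remedy.** With 5-10 components there are 5-10 interaction tests. If these are independent at 0.05, the chance of at least one false positive is 1 − 0.95^5 = 23% to 1 − 0.95^10 = 40%. Fitting all interactions in one model gave 23-26% with 5 components and 51-53% with 10. A joint model with 10 components has 10 + 1 + 10 = 21 coefficients for about 24 events.

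**The case against.** The strongest reply is that the metabolomics section gives one clause and no covariate list, so its silence should not be read as a specification. The section just before it says how the crossover is handled for this same endpoint, and that may be meant to carry over. This stands in part: the plan permits the error but does not prescribe it. It does not remove the point, because the term that would carry over is a main effect, and the component rows barely move when it is added.

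A reader might infer that the LVESVI regression has the same fault. The documents do not support that. The primary analysis compares the ON and OFF conditions within patients and refers to ON-OFF differences, so the natural reading of the LVESVI endpoint is that difference. The metabolomics section does not define its dependent variable, which is an ambiguity only. The finding that 42% of patients lost LVEF within two years does not change this: it concerns LVEF, over two years, in the 485 of 1,436 patients with follow-up echocardiography.

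A reader might also infer that the trial's main result is compromised. It is not. The primary endpoint and every power figure concern the paired LVESVI test, and the component work is introduced as exploration in a study labelled a pilot. Objective 3d is properly answered by a main effect.

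Finally, the simulated percentages are the power of a prognostic test under chosen inputs, with continuous event times, whereas echocardiography and biomarker blood draws after implant are scheduled at 6 and 12 months. That is a fair limit on the figures. It leaves the distinction between β and δ untouched.

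**Conclusion.** The point holds for the Cox analysis. As written, and also with the ON/OFF main effect added, the model estimates prognosis while the plan calls the result response to CRT. A purely prognostic marker can be reported as a predictor of response; the documents do not show that it will be. With 80 patients, CRT HR 0.7, event risk 17-30% and marker HR 1.3-1.6 per SD, this happens in about 15-60% of trials for a given marker, against 4-6% for one interaction test. Stronger markers or more events give higher figures. Apart from the partial guide for the 17%, these inputs are assumptions, so the range illustrates the problem and is not a forecast. The LVESVI regression needs a clarification only, and the primary test is unaffected.

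**What to change.** In Metabolomics data analysis and in the synopsis:

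- For the clinical endpoint, use the model already described for the composite (time-dependent ON/OFF, with period) and assess response to CRT by the interaction of each pre-implant component score with ON/OFF.
- Test one component at a time with multiplicity control, for example Holm or a permutation test. Report estimates with intervals and label the analysis exploratory.
- Report component main effects only under objective 3d, as prognosis.
- As a clarification, state that the LVESVI regression uses the within-patient ON-minus-OFF difference, with a period term.

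No new data are needed, and the metabolomic analysis is timed for after all subjects have completed study procedures. The cost is 5-10 extra interaction terms on few events, and so low power: in simulation, 46% with n = 100 and 30% risk for a marker with HR 0.5 per SD when ON and 1.0 when OFF. The plan rules out a washout after implantation and states none at the 6-month switch, so carry-over remains a caveat for any ON/OFF contrast.
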